## 11.3 Statistical criteria of termination of the investigation

Only data from subjects who have completed the entire protocol will be included in the study. This ensures that all data has been collected under the same conditions and thus remains homogeneous and comparable.

## 11.4 Planned Analyses

### 11.4.1 Datasets to be analysed, analysis populations

Only complete data sets will be included in the study. Data that contains only part of the protocol is not included in the analysis. No new subjects are being sought to replace the missing data.

### 11.4.2 Primary Analysis

The statistical data analysis will be carried out by [name] after completion of the data collection of the entire project.

Repeated measures analysis of variance (MANOVA) 2

factors:

Factor 1: Intervention (Game Ready vs. Control Intervention)

Factor 2: Time (baseline, 4th postoperative day and 6 weeks)

The significance level is set to  $p < 0.05$ . Statistical data analysis is carried out with SPSS.

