----------------------------------	---

Objective(s):	
In this study, the effect of repeated cold application with dynamic compression with the Game Ready and a control group will be investigated. The influence of these interventions and their effects will be investigated after a total knee endoprosthesis operation has been performed during the hospital stay. The change in the following parameters is examined: questionnaire on everyday activity and patient satisfaction, joint circumference in mm, skin temperature in C°, range of motion in degrees, morphine consumption in number per day, Pain sensation with the VAS, the length of the days of stay, the 10-meter walking test and the timed up-and-go in seconds.
 
The aim is to determine the effects of cold application with dynamic compression in order to be able to make recommendations. The current scientific knowledge requires further studies to substantiate or refute effects that have already been established.

Outcome(s):	
Primary outcomes
 
 
-Questionnaire Everyday Activity [Score]
 
-Patient satisfaction [cm]
 
-Joint circumference [mm]
 
-Range of motion [degrees]
 
-Skin temperature [°C]
 
-Morphine consumption [number]
 
- Visual analog pain scale [cm]
 
-Duration of stay [days]
 
-10-meter walk test[s]
 
-Timed-Up-and-Go [s]
 

Design:	Randomized, controlled trial

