Intervention:	
The Game Ready GR PRO 2.1 is a certified product that complies with European regulations, directives and standards.
 
The system can administer ice-free cold treatment and intermittent pneumatic compression treatment, providing healthcare professionals with options for different patients, procedures, injuries and rehabilitation stages.
 
The following intervention is performed according to the manufacturer's protocol for patients with primary total knee arthroplasty: 48 hours after the operation starts the Game Ready Intervention, if tolerable, with little compression (level 1 = 5-15 mmHg) and cooling at the coldest level tolerable by the participant (corresponds to program 2). The cooling should be perceived as "pleasant" by the participant. The intervention lasts one hour, of which 30 minutes are on and 30 minutes off cycles. The on cycle includes the duration of the intervention (cooling and compression), while the off cycles include the rest period. After 60 minutes, the device is removed. If compression is not tolerated, it can also be omitted (corresponds to program 1). The intervention is performed twice a day for the first four days after surgery. The coldest tolerable temperature level is determined anew with each treatment. The compression level can be increased depending on the participant. Medium compression may only be applied from the second day onwards (corresponds to programme 3).

Control intervention (if applicable):	
In order to obtain high-quality study results, the test subjects are exposed to only one experimental condition at a time. There are two groups. In order to maintain the quality of the study, a randomized controlled trial design will be chosen. The division into the groups is randomized. The data collected in this way is pooled by outcome or group.
 
The control group will receive ordinary physiotherapy treatment, without Game Ready application.

Number of subjects with rationale:	
n=28 (14 per group) G-Power analysis: effect size at 0.8

Duration of the investigation:	
May 2022 – December 2024

Investigation schedule:	
May 2022- subject –In (planned) June 2023- subject –Out (planned)

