Investigator(s):	
Examiner:          [name] 1,2,3          [name] 1,2,3          [name] 2          [name] 2          [name] 2          [name] 2          1 University College Physiotherapy Thim van der Laan, [name]          2 University of Applied Sciences and Arts Southern Switzerland, Rehabilitation and Exercise Science Laboratory (RESlab), Department of Business Economics, Health and Social Care, Physiotherapy Graubünden, [name]          3 Vrije Universiteit Brussels, Faculty of Physical Education and Physical Therapy, [name]
 
Contact / Principal Investigator:          [name]          University of Applied Sciences and Arts Southern Switzerland          Physiotherapy Graubünden          [name] [name] [name]          [contact]

Investigational Site(s):	
Single-centric investigation:          Regionalspital Surselva AG          [name]          [name]

Statistical considerations:	
Repeated measure ANOVA          Two-way          Bonferroni correction          Factors:          -Task          -Time          The significance level is set at <math>p<0.05</math>, and the statistical data analysis is carried out with SPSS.

Compliance statement:	
This investigation will be conducted in compliance with the CIP, the current version of the Declaration of Helsinki, ISO14155, ICH-GCP (as far as applicable) as well as all national legal and regulatory requirements.

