### 4.2 Primary Objective

In this project, the effect of postoperative cooling on physiological parameters is measured and compared with the control group.

- Physical Function [Score]
- Patient satisfaction [cm]
- Joint circumference [mm]
- Range of motion [degrees]
- Skin temperature [°C]
- Morphine consumption [number]
- Visual analog scale [cm]
- Length of stay [days]
- 10-meter walk test [sec]
- Timed-Up-and-Go [sec]

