## **5.2 Secondary outcomes**

None available.

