#### Visual analog scale [cm]

H0: The sensation of pain with the Visual Analog scale is not reduced by cryotherapy with intermittent dynamic compression compared to the control group during a hospital stay.

H1: The sensation of pain with the Visual analog scale is reduced by cryotherapy with intermittent dynamic compression compared to the control group during a hospital stay.

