## 11.2 Determination of Sample Size

A power analysis was performed using the G\*Power App (Düsseldorf, North Rhine-Westphalia, DEU), where a minimum number of 28 subjects was deemed necessary to ensure the statistical power (0.95) to detect a parameter difference at the 5% significance level. The figure below shows the G-Power calculation that was used to determine the sample size.

*Figure 4: Sample Size Calculation*

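### Ten outcomes are all primary, no rule controls error across them, and the sample size uses an undivided 5% level

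*Combined protocol and SAP*

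**What the plan says.** The synopsis lists ten outcomes under "Primary outcomes". Section 4.2 repeats them beneath an objective in which "the effect of postoperative cooling on physiological parameters is measured and compared with the control group", and section 5.1 describes each one. Section 5.1 also fixes the 4th postoperative day as the main time point, but for every parameter alike. Section 5.2 gives the secondary outcomes as "None available".

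Section 11.1 sets separate null and alternative hypotheses outcome by outcome, for example for pain: "H1: The sensation of pain with the Visual analog scale is reduced by cryotherapy with intermittent dynamic compression compared to the control group".

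Section 11.4.2 gives one model with two factors, "Factor 1: Intervention (Game Ready vs. Control Intervention") and time at three points, and a significance level of p<0.05. The synopsis adds "Bonferroni correction" beside the factors task and time. Section 11 does not mention it.

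Section 11.2 justifies 28 patients "to ensure the statistical power (0.95) to detect a parameter difference at the 5% significance level". The synopsis gives "effect size at 0.8" without naming the metric.

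**The concern.** Nothing in the plan says which outcome, or how many, must succeed for the trial to be positive. The two words on Bonferroni do not settle this. They could refer to pairwise time contrasts, which would leave the outcomes unadjusted, or to the outcomes, in which case the 5% level behind the sample size is not the level that will be used.

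The stated aim is to support treatment recommendations. As written, one chance result among several primary outcomes could be reported as a positive primary finding, and the outcome to emphasise could be chosen after the data are seen.

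**Working it through.** **How many outcomes can be tested between groups**

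- Ten are listed. Satisfaction is asked only of the Game Ready group (5.1), which leaves 9.
- Morphine count and length of stay have hypotheses (11.1) but no preoperative value in the visit table (9.1). They do not fit the three-time model, which leaves 7.
- Range of motion fits the model, but the available text of 11.1 shows no hypothesis for it. That leaves 6 with both a hypothesis and all three time points: KOOS, circumference, skin temperature, pain, 10-metre walk and Timed-Up-and-Go.

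The count K therefore runs from 6 to 9 at one test per outcome. It could be higher: circumference has seven sites and skin temperature four, on both sides, with no summary value named.

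**The plan's own figure**

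G*Power's settings are in a figure that is not shown, so the metric of 0.8 is an assumption. Read it as f(V) in a repeated-measures MANOVA interaction for one outcome, with 2 groups and 3 times: df1 = 2, df2 = N − 3, noncentrality λ = N × 0.8² = 0.64N.

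- N = 27: power 0.947.
- N = 28: λ = 17.92, df2 = 25, power 0.955.

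So 28 is the first N to reach 0.95, with one outcome and α = 0.05 undivided. With λ = df2 × 0.64 instead, N = 31 is needed.

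**If Bonferroni does not cover the outcomes**

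Each outcome is tested at 0.05. For independent tests, the chance of at least one false positive is 1 − 0.95^K. For correlated outcomes I assume equicorrelated normal statistics, one degree of freedom and two-sided tests, by numerical integration.

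| K | independent | ρ = 0.3 | ρ = 0.5 | ρ = 0.7 |
|---|---|---|---|---|
| 6 | 0.265 | 0.241 | 0.207 | 0.164 |
| 7 | 0.302 | 0.271 | 0.230 | 0.178 |
| 8 | 0.337 | 0.300 | 0.250 | 0.191 |
| 9 | 0.370 | 0.326 | 0.269 | 0.202 |

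If the deciding tests are one-degree-of-freedom group comparisons, the chance of at least one error favouring the device is 1 − 0.975^K when independent: 0.141 for K = 6 and 0.204 for K = 9. At ρ = 0.3 to 0.7 it lies between 0.165 (K = 9, ρ = 0.3) and 0.082 (K = 6, ρ = 0.7).

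**If Bonferroni covers the outcomes**

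Power at N = 28 and α = 0.05/K, under two readings of 0.8. The second is a two-sided two-sample t test with 14 per arm.

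| α | f(V) = 0.8, interaction | d = 0.8, t test |
|---|---|---|
| 0.05 | 0.955 | 0.53 |
| 0.05/6 | 0.81 | 0.25 |
| 0.05/7 | 0.79 | 0.24 |
| 0.05/8 | 0.78 | 0.22 |
| 0.05/9 | 0.77 | 0.21 |

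The Cohen's d reading does not reproduce the plan's N: power 0.95 would need 42 per arm, 84 in total. It is shown because a simple two-group comparison on day 4 is a natural single primary test. With 14 per arm, such a test at two-sided 0.05 has 0.80 power only for d of about 1.10, and 0.95 power only for d of about 1.42.

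**The case against.** **MANOVA could be one joint test of all outcomes.** This does not stand. Section 11.4.2 lists only intervention and time as factors, section 11.1 has separate hypotheses, and N = 28 reproduces as a single outcome measured three times.

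**Bonferroni is already planned.** It is named, but without a family, a number of tests or an adjusted level. Either reading leaves something to correct.

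**The one-degree-of-freedom figures do not describe the stated model.** This stands. The group-by-time interaction has two degrees of freedom and no single direction. The correlated rates and the share favouring the device therefore apply only if the outcomes are judged by group comparisons. The independent rates do not depend on this.

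**The Cohen's d powers conflict with N = 28.** This also stands. They illustrate a possible replacement test and are not the plan's calculation.

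**The harm is limited.** The outcomes are pre-listed, section 11.4.5 requires deviations to be justified and reported, and section 10.3 describes the study as basic research. A dropped outcome would be visible. But choosing which of several declared primary outcomes to emphasise is not a deviation, and the plan also states formal hypotheses, 0.95 power and an aim of making recommendations.

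**Conclusion.** The concern holds and should be fixed before analysis. Which failure applies depends on what Bonferroni was meant to cover, and the plan does not say.

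- If it does not cover the outcomes, the familywise error is about 26-37% for six to nine independent tests, or 16-33% at assumed correlations of 0.3-0.7, against a nominal 5%.
- If it does, the stated 0.95 power is not the power of the analysis. It is about 0.77-0.81 on the reading that reproduces N = 28.

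The power figures rest on an inferred metric for 0.8, and the correlations are assumptions. The missing multiplicity rule and the undivided 5% are read directly from the documents and depend on neither.

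**What to change.** In section 5.1, section 11.4.2 and the synopsis, name one outcome on the 4th postoperative day as the single primary, tested between groups at two-sided 0.05. Make the other eight outcomes with between-group data secondary, with Holm adjustment across them. Labelling them exploratory would also close the gap. State power for that specific test with its effect-size metric, since 0.95 does not carry over.

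Alternatively, keep several primaries, name the family, apply Holm, and replace 0.95 with the power of each test actually used. Power at 0.05/K is a conservative figure for Holm.

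Either way:

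- Pre-specify one operated-side summary value for circumference and one for skin temperature, at the sponsor's choice.
- Compare morphine count and length of stay between groups without the time factor.
- Report satisfaction descriptively.
- Say what the Bonferroni correction covers, or remove it.

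The cost is wording, a less favourable stated power and a stricter threshold for the non-primary outcomes. No extra patients are needed if the lower power is accepted. Keeping 0.95 with a Bonferroni-adjusted family of six to nine would need 39-41 patients on the f(V) reading, or 40-42 in equal arms.

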## 5. CLINICAL INVESTIGATION OUTCOMES

### 5.1 Primary Outcome

This study aims to investigate the effects of cryotherapy with intermittent dynamic compression with Game Ready during a hospital stay. The preoperative measurement is the baseline, the 4th postoperative day is the primary endpoint and the measurement 6 weeks postoperative is declared as follow-up. The following parameters are examined for this purpose:

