#### Patient satisfaction [cm]

In order to evaluate the patient satisfaction of the intervention group (Game Ready), the test subjects are asked the question "How satisfied are you with the cooling intervention?" immediately after the intervention. With the help of the Visual Analog Scale, the test subjects rate their satisfaction with a number between 0 (not at all satisfied) and 10 (maximally satisfied). The measurement moments take place twice a day (each time after the cooling intervention) during the

hospital stay.

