#### Patient satisfaction [cm]

In order to evaluate the patient satisfaction of the intervention group (Game Ready), the test subjects are asked the question "How satisfied are you with the cooling intervention?" immediately after the intervention. With the help of the Visual Analog Scale, the test subjects rate their satisfaction with a number between 0 (not at all satisfied) and 10 (maximally satisfied). The measurement moments take place twice a day (each time after the cooling intervention) during the hospital stay.

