## **11. STATISTICAL METHODS**

### **11.1 Hypothesis**

Physical Function [AU]

H0: The use of cryotherapy with intermittent dynamic compression has no positive effect on the physical functions of patients after a total knee arthroplasty.

H1: The use of cryotherapy with intermittent dynamic compression has a positive effect on the physical functions of patients after a total knee arthroplasty.

Patient satisfaction [cm]

H0: The use of cryotherapy with intermittent dynamic compression has no positive effect on patient satisfaction of patients after a total knee arthroplasty.

H1: The use of cryotherapy with intermittent dynamic compression has a positive effect on patient satisfaction of patients after a total knee arthroplasty.

Joint circumference [mm]

H0: The joint circumference is not reduced by cryotherapy with intermittent dynamic compression compared to the control group during a hospital stay.

H1: The joint circumference is reduced by cryotherapy with intermittent dynamic compression compared to the control group during a hospital stay.

Skin temperature [C°]

H0: The skin temperature is not reduced by cryotherapy with intermittent dynamic compression compared to the control group during a hospital stay.

H1: The skin temperature is reduced by cryotherapy with intermittent dynamic compression compared to the control group during a hospital stay.

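### The primary analysis names no test of the declared Day-4 endpoint, and its three-level time factor does not fit three of the ten primary outcomes

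*Combined protocol and SAP*

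**What the plan says.** Section 5.1 sets the time points: "the 4th postoperative day is the primary endpoint", and "the measurement 6 weeks postoperative is declared as follow-up". Ten outcomes are listed as primary and none as secondary.

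Section 11.4.2 gives one repeated-measures model for all of them. It has a two-level group factor and "Factor 2: Time (baseline, 4th postoperative day and 6 weeks", at a 5% level. It does not say which term decides the trial. Section 11.4.3 replaces arm by side of the body and keeps the same three times. The synopsis lists a two-way repeated-measures ANOVA with a Bonferroni correction, without saying which comparisons the correction covers. Section 11.4.2 does not repeat it.

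The measurement schedules differ by outcome:

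- **Seven outcomes** (KOOS, circumference, range of motion, skin temperature, pain VAS, 10-metre walk, timed-up-and-go) are scheduled preoperatively, on Day 4 and at six weeks. For the 10-metre walk this rests on section 9.2.1, because section 5.1 gives a four-week moment instead of Day 4.
- **Satisfaction** has the stated purpose "In order to evaluate the patient satisfaction of the intervention group (Game Ready", and "The measurement moments take place twice a day (each time after the cooling intervention". The two-arm test log in section 9.1 lists it for the cooling group only. Section 11.1 nevertheless has an alternative hypothesis that the treatment "has a positive effect on patient satisfaction of patients after a total knee arthroplasty".
- **Length of stay** is one number per patient.
- **Morphine** is a per-day count with no preoperative value in the test log. Its hypothesis is limited to the hospital stay.

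Section 4.2 lists "Range of motion [degrees]" among the primary parameters, but section 11.1 has no hypothesis for it. Section 11.1 has nine hypotheses in all, six of them for the seven repeated outcomes. Five of those six, such as pain, are framed as "compared to the control group during a hospital stay".

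**The concern.** The declared question concerns one time point, while the declared model spans three and names no deciding term. Several results could then be reported as the primary result: the interaction, the group main effect, or a Day-4 contrast from the fitted model. They answer different questions. The interaction asks whether the arms' profiles differ anywhere across the three times, so a real difference at six weeks alone can make it significant. The group main effect averages in the preoperative value, where randomised arms should not differ.

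For satisfaction the problem is the data: with no control values, no model can estimate a between-arm effect. For length of stay and morphine the time factor has nothing to act on as defined. At stake is whether a positive trial would show an effect at the endpoint it declared.

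**Working it through.** **Inputs from the protocol.** 14 per arm (section 6.1), effect size 0.8 with no metric given (synopsis), power 0.95 and a 5% level (section 11.2).

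**Assumptions not in the protocol.** Equal SDs, compound symmetry, correlation ρ of 0.3, 0.5 or 0.7 between time points, and all 28 patients analysed.

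**Step 1. The plan's own figure.** Read 0.8 as f(V) for a repeated-measures MANOVA interaction with two groups and three times. Then λ = f²N, with 2 and N − 3 degrees of freedom.

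- N = 27: λ = 0.64 × 27 = 17.28, power 0.947
- N = 28: λ = 0.64 × 28 = 17.92, power 0.955

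The minimum is 28, as stated. This is an inference, because the G\*Power figure is not shown. Other noncentrality conventions give 30 to 31. A two-sample t-test with 0.8 in SD units needs 42 per arm.

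**Step 2. Is the interaction specific to Day 4?** Let δ_j be the between-arm difference in SDs at time j. Then λ = (n/2) Σ(δ_j − δ̄)² / (1 − ρ), with 2 and 52 degrees of freedom. For an effect of 0.8 at six weeks only, Σ(δ_j − δ̄)² = 0.64 × 2/3 = 0.427, so λ = 7 × 0.427/(1 − ρ) = 2.987/(1 − ρ).

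| ρ | λ | Interaction power | Day-4 ANCOVA rejections |
|---|---|---|---|
| 0.3 | 4.27 | 0.42 | 0.05 |
| 0.5 | 5.97 | 0.56 | 0.05 |
| 0.7 | 9.96 | 0.79 | 0.05 |

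Simulation agrees (about 41 to 79%). An effect of 0.8 at Day 4 only gives the same λ, so the interaction cannot tell the two situations apart. The multivariate form (2 and 25 degrees of freedom) gives 0.40, 0.53 and 0.76.

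**Step 3. The group main effect.** Here λ = (n/2) δ̄² / [(1 + 2ρ)/3], with 1 and 26 degrees of freedom. A Day-4-only effect of 0.8 gives δ̄ = 0.8/3 = 0.267 and power of 0.15, 0.13 and 0.12.

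**Step 4. How often would the choice of test matter?** For a Day-4-only effect, setting 17.92 = 7 × (2/3) d² / (1 − ρ) gives d = 1.64, 1.39 and 1.07 SD at the three correlations. The table compares the interaction with a two-sided Day-4 ANCOVA at 5%, 20,000 simulated trials per scenario. The six-week effect is none, half or all of the Day-4 effect. The last column is the share of trials in which exactly one of the two tests is significant.

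| Reading of 0.8 | ρ | Day-4 effect (SD) | Interaction power | ANCOVA power | Tests differ |
|---|---|---|---|---|---|
| f(V) | 0.3 | 1.64 | 0.97/0.90/0.97 | 0.99 | 3/9/4% |
| f(V) | 0.5 | 1.39 | 0.97/0.90/0.97 | 0.98 | 3/8/4% |
| f(V) | 0.7 | 1.07 | 0.97/0.90/0.97 | 0.96 | 4/7/5% |
| SD units | 0.3 | 0.8 | 0.42/0.32/0.42 | 0.55 | 27/31/35% |
| SD units | 0.5 | 0.8 | 0.56/0.44/0.56 | 0.63 | 23/28/29% |
| SD units | 0.7 | 0.8 | 0.79/0.66/0.79 | 0.80 | 15/19/18% |

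Under f(V) the largest loss of power is 0.99 − 0.90 = 9 points. The multivariate form moves these figures slightly: under f(V) the tests differ in up to 11% of trials and the largest loss is about 10 points.

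**Step 5. Which outcomes fit the model?** Seven of the ten have both arms and all three times. Satisfaction lacks the control arm and the three times. Length of stay and morphine have both arms but not the three times. So 10 − 3 = 7 fit.

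**The case against.** The strongest reply is that the intent is plain. Section 5.1 names Day 4 and calls six weeks follow-up, most hypotheses refer to the hospital stay, and the statistician is blinded (section 6.2.2). On this view one contrast is missing and little else. It is fair that the intent is readable, but neither the synopsis nor section 11.4.3 supplies the missing test.

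It can also be said that length of stay and morphine are not untestable, because the group factor reduces to an ordinary two-group comparison. That stands: the test is unstated, not unavailable. The satisfaction hypothesis also does not name a control group, so the between-arm comparison is implied. But an effect of the device on satisfaction cannot be shown from treated patients alone.

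A reader might infer three stronger things that the protocol does not support:

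- **That the trial is underpowered or N = 28 is wrong.** The one reading found to reproduce 28 at power 0.95 is f(V) = 0.8 for the interaction. There the two tests seldom differ. The 15 to 35% applies only if 0.8 is in SD units, and it counts differences in significance, not opposite directions of effect.
- **That the protocol makes the interaction its test.** It does not; it names no term.
- **That the deciding term will be chosen after results are seen.** Section 12.4 has results and analyses presented monthly to the study supervisor. Section 11.4.2 places the analysis after data collection. Section 11.4.4 plans no additional interim analyses yet describes analysis in stages. These sections conflict, but they do not show a late choice.

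**Conclusion.** The point holds for all ten primary outcomes, in different ways. Seven have no named test of the declared endpoint, and one of these, range of motion, also lacks a hypothesis. Satisfaction has a hypothesis that its data cannot test. Length of stay and morphine need a group comparison that is not stated.

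The main consequence concerns which question is answered. If the interaction is used, a six-week-only difference of 0.8 SD would be significant in about 41 to 79% of trials with no Day-4 effect at all. Where a Day-4 effect exists, the choice between the interaction and a Day-4 ANCOVA changes significance in about 3 to 10% of trials under the reading that reproduces N = 28, with at most about 9 points of power lost (about 10 in the multivariate form). If 0.8 is in SD units, it changes significance in 15 to 35%. These figures rest on the assumed compound symmetry, the correlations and complete data. The mismatch between endpoint, data and model rests on the text alone. It should be corrected before analysis.

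**What to change.** Amend section 11.4.2 as follows.

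1. **Seven repeated outcomes.** Make the primary test the between-arm comparison at Day 4 by ANCOVA, with the preoperative value as covariate. A pre-named Day-4 group contrast within the planned model would also close the gap. Analyse six weeks as follow-up and keep the three-time model as secondary. Name one operated-side site or mean for circumference and for skin temperature. Add the range-of-motion hypothesis. State which tests the synopsis Bonferroni correction covers.
2. **Length of stay and morphine.** Compare length of stay, and one pre-specified in-hospital morphine total, between arms with a named two-group test, an estimated difference and a confidence interval.
3. **Satisfaction.** Delete its hypotheses and report it descriptively for the device arm.

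Reconcile the Day-4 and four-week timings of the 10-metre walk in sections 9.2.1 and 5.1. Reconcile sections 11.4.2 and 11.4.4 with the monthly presentation of results in section 12.4.

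The cost is an amendment with ethics committee review (section 2.10), and the omnibus test becomes secondary. No new patients, visits or data are needed.

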## 6. CLINICAL INVESTIGATION DESIGN

### 6.1 General clinical investigation design and justification of design

Randomized, controlled trial

It is a clinical investigation concerning medical devices (MD), Category according to Art 6 ClinO-MD (A1), whereby a CE-certified medical device is tested in the intervention group.

The group size of the participants is n=28 people (per group n=14 people). The group assignment is randomized.

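### Section 11.4.2 makes the preoperative value a level of Time, with no baseline covariate and no named Day-4 contrast, which usually costs precision at 14 per arm

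*Combined protocol and SAP*

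**What the plan says.** Section 5.1 assigns the three measurement times different roles: "The preoperative measurement is the baseline, the 4th postoperative day is the primary endpoint", and six weeks is follow-up.

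Section 11.4.2 gives the model as "Repeated measures analysis of variance (MANOVA) 2" factors. The first is "Factor 1: Intervention (Game Ready vs. Control Intervention"; the second is "Factor 2: Time (baseline, 4th postoperative day and 6 weeks". So the preoperative value is one of three repeated responses. No covariate is listed there, in the secondary analysis (11.4.3) or in the Synopsis. None of these places says whether the group main effect, the group-by-time interaction or a Day-4 comparison decides the question.

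On size, section 6.1 states "The group size of the participants is n=28 people (per group n=14 people". The Synopsis adds "G-Power analysis: effect size at 0.8", and section 11.2 says the number was chosen "to ensure the statistical power (0.95) to detect a parameter difference at the 5% significance level".

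By the test log in section 9.1, seven of the ten primary outcomes are measured at Visit 1: KOOS, circumference, range of motion, skin temperature, VAS pain, 10-metre walk and Timed-Up-and-Go. Satisfaction, morphine count and length of stay are not.

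**The concern.** The preoperative value is taken before treatment, so the device cannot affect it. In a group-by-time model, the Day-4-versus-baseline interaction contrast is the between-arm difference in change from baseline. That subtracts the whole baseline value, a slope of 1, for every outcome, however well or badly the preoperative value predicts Day 4. When the true slope is below 1, the subtraction adds noise, and any chance difference between the arms before surgery is over-corrected. With 14 per arm such differences are not small, and there is little precision to spare.

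**Working it through.** **The plan's own figure.** 28 reproduces if 0.8 is read as G*Power's f(V) for the repeated-measures MANOVA interaction with 2 groups and 3 times: df1 = 2, df2 = 28 − 3 = 25, λ = 28 × 0.8² = 17.92, α = 0.05. Power is 0.955 at N = 28 and 0.947 at N = 27. This reading is an inference, because the G*Power figure is not shown. It does not reproduce as a standardised mean difference of 0.8: a two-sided t-test would need 84 in total, and 28 gives power 0.53. The 0.8 SD used below is therefore an assumption of this check, not the plan's effect size.

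**Inputs.** n = 14 per arm (section 6.1) and α = 0.05 two-sided. Assumed: a Day-4 difference of 0.8 SD, a baseline-to-Day-4 correlation r of 0.3 to 0.7, and equal SDs at both times.

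**Variances**, in units of the Day-4 variance:
- Change score: 2(1 − r), with 26 df.
- ANCOVA: (1 − r²)(1 + 1/24), with 25 df. The factor 1 + 1/(N − 4) is the price of estimating the slope.
- Information lost by the change score: 1 − [(1 + r)/2 × 1.0417].
- Noncentrality for power: 0.8 × √7 / √variance.

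| r | variance, change | variance, ANCOVA | loss | 28 patients act like | power, change | power, ANCOVA |
|---|---|---|---|---|---|---|
| 0.3 | 1.40 | 0.948 | 32% | 19 | 0.41 | 0.55 |
| 0.5 | 1.00 | 0.781 | 22% | 22 | 0.53 | 0.63 |
| 0.7 | 0.60 | 0.531 | 11% | 25 | 0.75 | 0.80 |

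The sixth-last step, patients, is 28 × (1 − loss). Simulation with 40,000 trials per cell agrees, and the change-score test rejects in 4.9% to 5.1% of null trials.

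**Unequal SDs.** Let k be the Day-4 SD divided by the baseline SD. The large-sample loss is (1 − rk)²/(1 + k² − 2rk). For r = 0.3, 0.5, 0.7:
- k = 0.75: 54%, 48%, 44%.
- k = 1.5: 13%, 4%, 0.2%. With the small-sample factor, 1 − (1 − loss) × 1.0417, these become about 9%, 0% and −4%. In the last case ANCOVA is slightly worse.

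**Chance imbalance, equal SDs.** The baseline difference has standard error √(2/14) = 0.38 SD. The change-score estimate moves by −(1 − r) times that difference, and ANCOVA by about 0. A one-standard-error imbalance shifts the change score by 0.26, 0.19 and 0.11 SD at r = 0.3, 0.5 and 0.7. An imbalance above 0.5 SD has probability 0.19; one of exactly 0.5 SD at r = 0.3 shifts the estimate by 0.7 × 0.5 = 0.35 SD.

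**Other readings of 11.4.2:**
- The 2-df interaction, with the effect at Day 4 only, has power 0.40 to 0.42, 0.53 to 0.56 and 0.76 to 0.79 (multivariate to univariate form) at r = 0.3, 0.5 and 0.7. All are below ANCOVA.
- A Day-4 comparison that ignores baseline loses r² against ANCOVA in large samples: 9%, 25% and 49%.
- The group main effect averages in a value that the device cannot change.

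**The case against.** The case against is substantial.

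- *The planned test is valid.* This stands. A reader might infer that the analysis is biased, or that it leaves baseline imbalance uncorrected. Neither is so: a change score removes the whole imbalance and, with equal SDs, over-corrects it. The 0.35 SD shift is conditional on one particular imbalance; over randomisation the estimate is unbiased.
- *The size is not in the documents.* This stands. A reader might quote a loss of 15% to 40% as a property of the plan. That range is (1 − r)/2 for r from 0.7 down to 0.2, in large samples with equal SDs. A Day-4 SD well above the baseline SD could nearly remove it. Nor do the documents support saying that power is lost on every visit-based outcome, or which outcomes have strong or weak correlations.
- *The change score is only one reading.* This stands, and it is why the fix begins by naming the contrast. Every reading examined favours adjustment or leaves it nearly neutral.
- *At the plan's own effect the gap is small.* If 0.8 is f(V), the implied Day-4 difference is √(4 × 0.64 × 1.5 × (1 − r)), or 1.64, 1.39 and 1.07 SD at r = 0.3, 0.5 and 0.7 (equal correlations, effect at Day 4 only). Change-score power is then 0.94 against 0.99, 0.98 and 0.96 for ANCOVA. This stands for power at that large effect; the information loss, and so the wider confidence interval, is the same.

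**Conclusion.** The point holds as one of efficiency and specification, not of validity. Section 11.4.2 treats the baseline of section 5.1 as an outcome and leaves the Day-4 contrast unnamed. On the change-score reading, with equal SDs and r between 0.3 and 0.7, the trial gives up about 32% to 11% of its information at N = 28. For a 0.8 SD difference that is 14 to 5 points of power. These figures rest on an assumed r, SD ratio and effect. The direction is firmer than the size: the large-sample loss is never negative, and the worst case for adjustment is about 4%. The point covers seven of the ten primary outcomes. The change should be made before the data are analysed, so that adjusted and unadjusted results are not chosen between afterwards.

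**What to change.** In section 11.4.2:

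1. Name the between-arm difference at Day 4 as the primary contrast.
2. For KOOS, circumference, range of motion, skin temperature, VAS pain, 10-metre walk and Timed-Up-and-Go, remove baseline from the Time factor and enter the preoperative value of the same outcome as a covariate. Use either ANCOVA at Day 4 (arm and baseline), or a mixed model for Day 4 and week 6 with arm, time, arm × time, baseline and baseline × time. Report the adjusted Day-4 difference with its confidence interval.
3. State that satisfaction, morphine count and length of stay have no preoperative value and are outside this change.

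Section 11.2 must be reworded so that the sample-size statement refers to the changed model and says what its 0.8 measures. The cost is one error degree of freedom in the Day-4 ANCOVA, at worst about 4% of precision. No new data, visits or patients are needed, and SPSS fits either model.
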